## Part 2:

Approximately 50 participants will be recruited for Part 2, 25 AML participants and 25 HR-MDS participants. Part 2 cohort expansion is designed based on predictive probability methodology of Lee and Liu (Lee, 2008). A test that the overall response rate [ORR] (p) is less than or equal to the null hypothesis rate versus the response rate is greater than or equal to the alternative rate is being performed separately in each indication using the stopping rules shown in Table 15.

For Part 2 the hypotheses in terms of overall response rate (p) are detailed below.

The null hypothesis is:

H0: p≤10%

The alternative hypothesis is:

HA: p≥30%

The null hypothesis of p=10% was specified given low likelihood of response following failure of standard therapies. The alternative hypothesis of  $p\ge30\%$  was specified to ensure robust evidence for efficacy to support advancement of a novel drug.

GSK3745417 will be evaluated for efficacy in approximately 13 to 25 participants with AML and separately in 13 to 25 HR-MDS participants in the expansion cohorts.

The futility evaluation will occur after 13 participants have completed induction and allow for a maximum number of 25 participants. This design will have a type I error rate ( $\alpha$ ) of 0.09 and a power of 0.88. A cohort (AML and/or MDS) can be terminated early for futility if the predictive posterior probability of the response rate greater than the null hypothesis of 10% being above 80% is very low, i.e., below 10% ( $\theta$ L) for this design. The type I error rate and power were derived by explicitly stating null and alternative
hypotheses of response rate, the minimum and maximum sample size, boundaries of predictive probability for futility criteria and the selection of the optimizing criterion as the maximization of power under the alternative hypothesis. The Bayesian prior used in determining the design was Beta (0.01, 0.09), a distribution with a mean response rate of 10%. Under the null hypothesis, that is, if the true response rate is less than 10%, the expected sample size of the design is 17.5 participants per cohort and probability of early termination is 62.1%. Under the alternative hypothesis, that is, if the true response rate is at least 30%, the expected sample size of the design is 24.2 participants and probability of early termination is 6.4%.

### Table 15Stopping Rules for Part 2 Cohort Expansion

Number of Evaluable Participants a	Stop for Futility if No. of Responders Less Than or Equal to This Number b
13	1
25	4

a. Evaluable participants for response assessment are defined by any or all of the following criteria:

• Participants who have at least one post-baseline disease assessment.

• Participants who have progressed or have died or have withdrawn from study treatment due to any reason.

b. The specific criteria for stopping an expansion cohort due to futility. For instance, if 13 participants are enrolled, then the cohort may be stopped for futility if number of Responders ≤1.
Note: These rules will be applied to both AML and HP MDS cohorts in Part 2.

Note: These rules will be applied to both AML and HR-MDS cohorts in Part 2.

Enrollment into AML and/or HR-MDS cohorts in Part 2 may be stopped according to the rules in Table 15 once all enrolled participants in the expansion cohort have met criteria for evaluability (as defined in the footnote to Table 15) after induction. The futility stopping rules are intended as a guideline only. Actual decisions will depend on the totality of the data.

Up to 18 of these (AML and HR MDS) participants who respond to induction will continue to maintenance dosing. The maintenance dosing schedule will be determined based on data from the FTIH 208850 study. If enrollment into one of the cohorts (AML or HR MDS) is stopped early, additional participants in the other cohort may be enrolled to have a sufficient number of participants for maintenance dosing evaluation. Fewer doses in maintenance therapy are expected to be studied for dose escalation; therefore, the modified Toxicity Probability Interval (mTPI) procedure (Ji, 2013) (and not N-CRM) will be used to identify the MTD of GSK3745417 during maintenance dosing after 2 to 3 cycles of daily dosing at the induction MTD determined from Part 1. Part 2 will evaluate 3 increasing dose levels starting at the MTD determined from Part 1. The DLT period for Part 2 will be 28 days starting at Day 1 of each cycle. Dose escalation will target 3 participants up to a target maximum of 6 at each dose level. Dose escalation will proceed until the MTD for GSK3745417 in maintenance dosing is determined.

The rules guiding dose escalation based on the mTPI procedure are provided in Figure 8. Columns provide the number of participants treated at the current dose level, and rows provide the corresponding numbers of participants experiencing toxicity. The recommended decision (E = escalate to next higher dose, S = stay at current dose, D = de-escalate, DU = unacceptably toxic dose) is determined by taking the row showing the total number of participants with DLT at the current dose and finding the cell that

#### TMF- 14199778

#### CONFIDENTIAL

corresponds to the column showing total number of participants in the current dose level. For example, when one of three participants experiences a DLT at the current dose, the decision can be located at row indicating 1 and column indicating 3, which is S (to stay at the current dose level). All dose escalation decisions will be assessed by the GSK study team and investigators.

#### Figure 8 Dose Finding Spreadsheet of the Modified Toxicity Probability Interval (mTPI) Method

				NUIT	iber	OL	patie	ents	trea	itea	ato	curre	ento	lose	•	
		1	2	3	4	5	6	7	8	9	10	11	12	13	14	15
5	0	E	E	E	E	E	E	E	E	E	E	E	E	E	E	E
	1	D	S	S	S	S	E	E	E	E	E	E	E	E	E	E
2	2		DU	D	S	S	S	S	S	S	S	E	E	E	E	E
3	3			DU	DU	D	S	S	S	S	S	S	S	S	S	S
5	4				DU	DU	DU	D	D	S	S	S	S	S	S	S
	5					DU	DU	DU	DU	DU	D	S	S	S	S	S
	6						DU	DU	DU	DU	DU	DU	D	S	S	S
Ĩ	7							DU	DU	DU	DU	DU	DU	DU	D	S
	8								DU	DU	DU	DU	DU	DU	DU	DU
	9									DU	DU	DU	DU	DU	DU	DU
ŝ	10										DU	DU	DU	DU	DU	DU
	11											DU	DU	DU	DU	DU
2	12												DU	DU	DU	DU
	13													DU	DU	DU
	14	E = Escalate to the next higher dose									DU	DU				
	15		) – C	blay	atu	ie cu	urrer		se		daa	-				DU
			/ - L	ле-е	scar	ate	10 IN	e ne	XUIO	wer	405	е				
	U = The current dose is unacceptably toxic															
		- 1		= 31	J%											
		S	amp	ole S	ize =	= 15										
		E	psil	on1	= 0.0	05										

The spreadsheet was generated based on a beta/binomial model and precalculated before trial initiation. The letters in different colors are computed based on the decision rules under the mTPI method and represent different dose-finding actions. In addition to actions de-escalate the dose (D), stay at the same dose (S), and escalate the dose (E), the table includes action unacceptable toxicity (DU), which is defined as the execution of the dose-exclusion rule in mTPI.

## 9.3. Analysis Sets

Population	Description	Analyses Evaluated
All screened	All participants who sign the ICF to participate in the clinical study. Participants in this population will be used for the screen failure summary.	Study Population
Safety	All participants who take at least 1 dose of study intervention. Participants will be analyzed according to the intervention they actually received.	Study Population, Safety, Efficacy
DLT-evaluable	All participants who take at least 1 dose of study intervention and are followed for the DLT observation period or are withdrawn within the DLT observation period due to meeting the DLT criteria.	Summary/Listing of Dose-Limiting Toxicities during the Determinative Period
PK population	All participants from the safety population for whom a PK sample is obtained and analyzed.	РК
PD population	All participants who contribute a predose and at least one on-treatment PD/biomarker sample(s).	PD

For purposes of analysis, the following populations are defined:

## 9.4. Statistical Analyses

The statistical analysis plan (SAP) will be finalized prior to FSFV and it will include a more technical and detailed description of the statistical analyses described in this section. This section is a summary of the planned statistical analyses of the most important endpoints including primary and key secondary endpoints.

Data will be listed and summarized according to the GSK reporting standards, where applicable. Complete details will be documented in the SAP. Any deviations from, or additions to, the original analysis plan described in this protocol will be documented in the SAP and clinical study report (CSR).

## 9.4.1. Efficacy Analyses

The safety population will be used for anticancer activity analyses. Since this is a Phase 1 study, anticancer activity will be evaluated based on clinical evidence and response criteria.

Overall response rate (ORR) for AML is defined as the percentage of participants with a complete remission (CR), CRp, CRi, or a partial remission (PR) as per response criteria for AML (Cheson, 2003) and HR MDS (Cheson, 2006), respectively. Participants with unknown or missing response will be included in the denominator when calculating the percentage.

The estimate of ORR along with 95% exact confidence interval (CI) will be provided.

Duration of response (DOR) for AML is defined as the time from first evidence of response to earlier date of disease progression or death due to any cause, for participants with a complete remission (CR), CRp, CRi, or a partial remission (PR) as per response criteria for acute myeloid leukemia. Participants who have not progressed or died at the data cut-off, will be censored at the date of last adequate disease assessment. In addition, participants with an extended time without adequate assessment or who start a new anticancer therapy prior to a DOR event will be censored at the date of last adequate disease assessment (assessment where visit level response is CR, CRp, CRi, or PR) prior to the extended time without adequate assessment or initiation of new anti-cancer therapy, respectively. Further details on rules for censoring will be provided in the Statistical Analysis Plan. DOR will be summarized using Kaplan-Meier quantile estimates along with 95% CIs.

Event-free survival (EFS) is defined as the time from first dose of study intervention to disease progression, failure to achieve CR, or relapse from CR, or death resulting from any cause, whichever occurs earliest. Participants who achieve induction treatment success and are alive and in remission at the data cut-off, will be censored at the date of last adequate disease assessment. In addition, participants with an extended time without adequate assessment or who start a new anticancer therapy prior to an EFS event will be censored at the date of last adequate disease assessment (assessment where visit level response is CR, CRp, CRi, PR, or SD) prior to the extended time without adequate assessment or initiation of new anti-cancer therapy, respectively. Further details on rules for censoring will be provided in the SAP. The milestone EFS at 6 months will be summarized using Kaplan-Meier quantile estimates along with 95% CIs.

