# 1. INTRODUCTION

The purpose of this SAP is to describe the planned analyses to be included in the Clinical Study Report (CSR) for Study 209809. Due to the termination of this study, only the planned Part 1 analyses described in the protocol will be produced for a synoptic CSR.

Additional details with regards to data handling conventions and the specification of data displays will be provided in the Output and Specification (OPS) document. Additional data will be available to view via RAPIDO DV (for more details see OPS).

[figure not shown]

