### 4. STATISTICAL ANALYSES

### 4.1. General Considerations

### 4.1.1. General Methodology

The Safety Analysis Set will be used for all study population, efficacy, and safety analyses, unless otherwise specified. AE and PK related tables, listings and figures will be summarized by dose level. Study population and efficacy tables and listings will be summarized by treatment sequence.

The DLT-evaluable Analysis Set will be used for assessment of dose-limiting toxicities.

Confidence intervals will use 95% confidence levels unless otherwise specified.

Unless otherwise specified, continuous data will be summarized using descriptive statistics: n, mean, standard deviation (std), median, minimum, and maximum. Categorical data will be summarized as the number and percentage of participants in each category.

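### The 6-month event-free survival milestone is to be summarized by Kaplan-Meier quantiles, which are times and do not give the 6-month event-free probability

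*Protocol*

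**What the plan says.** Protocol section 9.4.1 treats event-free survival (EFS) as a time-to-event variable: "Event-free survival (EFS) is defined as the time from first dose of study intervention to disease progression, failure to achieve CR, or relapse from CR", with death from any cause as the remaining event and the earliest of these counting. The paragraph closes with "The milestone EFS at 6 months will be summarized using Kaplan-Meier quantile estimates along with 95% CIs".

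The preceding paragraph, on duration of response (DOR), closes the same way: "DOR will be summarized using Kaplan-Meier quantile estimates along with 95% CIs".

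The EFS paragraph has two censoring rules. Participants with induction success who are alive and in remission at the data cut-off are censored at their last adequate assessment. Participants who have a long gap between assessments, or who start another anticancer therapy, before any EFS event are censored at the last adequate assessment before the gap or the new therapy. For this second rule an adequate assessment is an "assessment where visit level response is CR, CRp, CRi, PR, or SD". What the paragraph hands to the SAP is limited: "Further details on rules for censoring will be provided in the SAP".

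The SAP (section 1) states that after termination "only the planned Part 1 analyses described in the protocol will be produced for a synoptic CSR". Its table of contents lists section 4.4.1 on exploratory efficacy, but no text is visible under 4.4.

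**The concern.** The sentence names one quantity and prescribes an estimator of another. A programmer who follows it literally would produce the median and quartiles of EFS time, with intervals in months, and would neither report the proportion event-free at 6 months nor give it a confidence interval. The deferral to the SAP covers censoring, not the choice of estimator, so it does not repair this.

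The secondary matter is the failure event. Not reaching complete remission (CR) ends EFS, but the protocol does not say on which day. The second censoring rule applies only before an EFS event, so its reach depends on that unstated day.

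**Working it through.** The documents give no assumed 6-month EFS rate, event count or sample size for this endpoint, so there is no planned figure to reproduce. The check is one of definition, with an illustration under assumed curves.

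**1. The two quantities.** Let S(t) be the Kaplan-Meier estimate of the probability of being event-free at time t.
- Quantile: t_q = the smallest t with S(t) ≤ 1 − q. The result is a time in months.
- Milestone: S(6). The result is a probability.

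**2. Does a quantile fix S(6)?** Take Weibull curves with median m and shape k (both assumed). S(t) = exp{−(t/λ)^k} with λ = m/(ln 2)^(1/k), so S(6) = 2^(−(6/m)^k).

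| Median m (months) | Shape k | Time by which 75% have had an event (months) | S(6) |
|---|---|---|---|
| 2 | 0.6 | 6.35 | 26% |
| 2 | 1 | 4.00 | 12.5% |
| 2 | 1.6 | 3.08 | 2% |
| 4 | 0.6 | 12.7 | 41% |
| 4 | 1 | 8.00 | 35% |
| 4 | 1.6 | 6.17 | 27% |
| 6 | any of these | 9.25 to 19.05 | 50% |

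For example, m = 2 and k = 1 give 2^(−3) = 0.125. The same median goes with clearly different 6-month probabilities. Reporting the quartiles as well only brackets S(6): with m = 4, all three curves say no more than that it lies between 25% and 50%. A quantile gives S(6) exactly only when it falls at 6 months, as in the last row.

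**3. What the right statistic would look like.** Illustrative precision, with assumed outcomes, no censoring before 6 months and exact binomial 95% limits, for the approximately 22 participants planned in Part 1:
- 4 of 22 event-free: 18%, CI 5% to 40%.
- 7 of 22 event-free: 32%, CI 14% to 55%.

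The interval is wide, and it would be wider within the treatment sequences by which SAP section 4.1.1 groups efficacy tables.

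**4. The undated failure event.** Induction is 3 cycles of 28 days, so it ends at day 84 (3 × 28). Protocol section 4.1 allows additional cycles for participants with stable disease (SD) or partial remission (PR) after these 3 cycles. One more cycle would run to day 112 (84 + 28). Consider a participant with SD at day 84 who starts another therapy before day 112:
- If failure to achieve CR is dated at day 84, the event comes first and the participant has an event at day 84.
- If failure is declared only after the extra cycle, the new therapy comes first and the participant is censored at the day-84 assessment.

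The time is the same and the status is opposite. The visible text does not choose between them.

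**The case against.** The strongest reply is that this is a slip of wording with little consequence. The Kaplan-Meier fit needed for quantiles already contains S(6), section 9.4 calls itself a summary with full detail in the SAP, and SAP section 4.4.1 may already name the right estimator and date the failure event. EFS is not among the visible primary or secondary endpoints (the exploratory rows are redacted), no stopping rule or sample size uses it, and only Part 1 is reported. The SAP's partial-date rules (section 6.2.6) mention progression-free survival, response rate and duration of response but not EFS, so it is unclear that EFS will be analysed at all. This stands as a limit on severity. It does not make the protocol sentence correct.

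A reader might also infer that the protocol censors participants who failed to reach CR and so biases EFS upward, since PR and SD appear in the censoring text. The documents do not support that. Censoring at the data cut-off covers only those with induction success who are in remission. The PR and SD wording defines the last adequate assessment for participants with a gap or new therapy before any EFS event. Such visits occur naturally during induction, where response is assessed at days 28 and 56. Once failure is declared it is itself an event, and the earliest event counts. Only the missing date remains open.

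**Conclusion.** Minor, and wrong as written: the prescribed statistic does not estimate the quantity named. This rests on reading a 6-month milestone as the probability of being event-free at 6 months. The effect on a reported number cannot be sized from the documents. The spread of 2% to 26% at a common median of 2 months shows only that the two quantities are not interchangeable, and it depends on the assumed curves.

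The missing date for failure to achieve CR is a smaller, conditional point. It matters for participants with PR or SD who have an assessment gap or start new therapy around or after the end of induction, and it falls away if the SAP's exploratory section supplies the date. No claim is made that the SAP repeats the error, because that section cannot be seen.

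**What to change.** Replace the closing EFS sentence in protocol section 9.4.1 with: EFS at 6 months will be estimated by the Kaplan-Meier survival probability at 6 months with a 95% CI. A Greenwood variance with a log-log transform is one suitable interval; the 95% level agrees with SAP section 4.1.1. Quantiles of EFS time can be reported in addition.

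State the date on which failure to achieve CR is counted, including for participants given additional cycles, unless SAP section 4.4.1 already does so.

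The cost is a wording change with no new data. Since the study has ended, a note in the clinical study report would serve if SAP 4.4.1 already specifies the right estimator. If EFS will not be reported, saying so is enough.

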## 9.4.2. Safety Analyses

The safety population will be used for the analysis of safety data. All serially collected safety endpoints (e.g., laboratory tests, vital signs, ECGs) will be summarized according to the scheduled, nominal visit at which they were collected and across all on-treatment time points using a "worst-case" analysis. Complete details of the safety analyses will be provided in the SAP.

## 9.4.2.1. Extent of Exposure

The number of participants administered study intervention will be summarized according to the duration of therapy.

## 9.4.2.2. Adverse Events

AEs will be coded using the standard MedDRA and grouped by system organ class. AEs will be graded by the investigator according to the NCI-CTCAE (version 5.0). Events will be summarized with frequency and percentage by preferred term. Separate summaries will be provided for all AEs regardless of grade, treatment-related AEs, treatment-related AEs by maximum grade, serious adverse events (SAEs), treatment-related SAEs, AEs leading to discontinuation of study intervention, AEs leading to dose reductions and AEs leading to dose interruptions/delays. Details will be provided in the statistical analysis plan (SAP). Dose-limiting toxicities (DLTs) will be listed and summarized by dose cohort based on the DLT Evaluable Population. Any AEs

of special interest will be summarized as detailed in the SAP. The incidence of deaths and the primary cause of death will be summarized.

## 9.4.2.3. Clinical Laboratory Evaluations

Hematology and clinical chemistry data will be summarized using frequencies and proportions according to NCI-CTCAE v5. Laboratory test results outside the reference ranges that do not have associated NCI-CTCAE v5 criteria will be summarized using proportions. Further details will be provided in the SAP.

## 9.4.2.4. Other Safety Analyses

Data for vital signs and ECGs will be summarized based on predetermined criteria identified to be of potential clinical concern. Further details will be provided in the SAP.

## 9.4.3. Other Analyses

PK, PD, , and biomarker exploratory analyses will be described in the SAP. The population PK, PD, analyses may be presented separately from the main CSR.

## 9.4.3.1. Pharmacokinetic Analyses

PK analysis of GSK3745417 will be the responsibility of the Clinical Pharmacology Modeling and Simulation (CPMS) Department, GSK.

- PK analysis of GSK3745417 drug concentration-time data will be conducted by noncompartmental methods under the direction of CPMS, GSK. The following PK parameters will be determined if data permit:
  - o Cmax
  - area under the plasma concentration-time curve (AUC(0-t), AUC(0-t), [repeat dosing] and/or AUC(0- $\infty$ ) [single dose])
  - $\circ$  apparent terminal phase elimination rate constant ( $\lambda_z$ )
  - apparent terminal phase half-life  $(t_{1/2})$  (single dose)
  - systemic clearance of parent drug (CL)
  - volume of distribution (V)
  - Other parameters and analyses as appropriate and data permits, such as dose proportionality and time-invariance.

Statistical analyses of the PK parameters data will be the responsibility of Clinical Statistics, GSK. All PK analyses will be performed on the PK population.

Drug concentration-time data will be listed for each participant and summarized by descriptive statistics at each time point by cohort. PK parameter data will be listed for each participant and summarized by descriptive statistics by cohort and dosing day.

The data from this study may be combined with the data from other studies for a population PK analysis and/or exposure-response analysis, which will be reported separately.

